8.4 Multi-Institution Study Coordination

8.4.1 Personnel

At each site, personnel dedicated to this protocol will be:

- A study PI
- A research coordinator
- A data manager

In addition, at Lombardi-Georgetown, there will be a dedicated “multi-institutional” research coordinator who will play the primary role in coordinating the trial between Lombardi-Georgetown and additional sites. This coordinator will be the main point of contact for [name] and the other site PIs for any study related concerns, and to screen each patient being considered for enrollment (Including “remote” screening for the patients being screened at other sites). This coordinator will also be the point of contact for the data managers for data entry questions. Finally, this coordinator will play a major role in regulatory coordination of the study, specifically by: 1) Reviewing and confirming all study-related adverse events; 2) Submitting all SAE reports to the Georgetown IRB (The research coordinators at the other sites will prepare SAE reports for patients treated at their respective sites, but the “multi-institutional” coordinator will submit the final report); 3) Gathering and preparing all primary source data for review/audit by Theradex, Inc.

8.4.2. Patient Enrollment

Enrollment at the sites will be competitive. If a patient is being screened for enrollment, the local research coordinator must send an email within 24 hours containing the patient’s name, to the local PI, to [name], and to the multi-institutional coordinator. If a patient is successfully screened, the local research coordinator must send all supporting documentation to the multi-institutional research coordinator (by email or fax). Patients should not start therapy until both [name] and the multi-institutional coordinator have reviewed the patient’s records and confirmed that the patient is indeed eligible for enrollment.

8.4.3. Data Collection and Management

Patient data will be entered into the on-line accessible database. This database is housed at Lombardi-Georgetown, but is accessible anywhere there is internet access. The data manager and research coordinator at each site will attend an on-line training session so that they may learn how to enroll data into the data base. All screening data should be entered prior to starting therapy, and all ongoing patient data should be entered within one week of each patient visit.

8.4.4 Conference Calls

A monthly conference call will be held between Lombardi-Georgetown and the other sites to review patient enrollment, toxicity, and response assessment.

8.4.5. Trial Auditing

Theradex, Inc will provide trial auditing at Lombardi-Georgetown. The multi-institutional coordinator will arrange all primary source documents for the patients to be audited. This will include collecting copies of the primary source data for any patients treated at other sites.

8.5 Removal of Subjects from Therapy or Assessment

Each subject has the right to withdraw from study treatment at any time. In addition, the investigator may discontinue a subject from the study treatment at any time for any reason if the investigator considers it necessary, including the occurrence of an adverse event or noncompliance with the protocol. Each subject will be withdrawn from the study if any of the following occur:

- 1) The subject experiences either clinical or radiographic progressive disease.
- 2) The subject requires radiotherapy or alternate antineoplastic agents during the study period.
- 3) The investigator believes it is in the best interest of the subject.
- 4) Clinically significant deterioration of the subject's medical status as determined by the investigator.
- 5) The subject requires alternative anti-cancer agents or non-palliative radiation therapy for primary or metastatic disease during the treatment portion of the study.
- 6) Subject becomes pregnant or begins breastfeeding during the treatment portion of the study.
- 7) The subject or subject's legally acceptable representative decides to withdraw consent for any reason.
- 8) Any other medical reason that the study investigator deems appropriate.

8.5.1 Discontinuation of Individual Subjects

When a subject discontinuation from the study (without reaching a protocol-defined endpoint) is planned, the investigator will notify the clinical team representative via telephone as soon as possible (provided, in each case, subject care and safety are not compromised). When a subject discontinues the study, a Final Visit will be conducted (preferably prior to the initiation of another anticancer therapy). However, these procedures should not interfere with the initiation of any new treatments or therapeutic modalities that the investigator feels are necessary to treat the subject's condition. Following discontinuation of the study drug, the subject will be treated in accordance with the investigator's best clinical judgment. At the Final Visit, the reason(s) for the discontinuation from the study will be recorded and a physical examination including neurologic assessment, body weight, vital signs measurement, laboratory analyses, performance status, tumor assessment, collection of unused study drug and an assessment of adverse events will be performed as soon as possible after discontinuation from the study. All subjects will have one Follow-Up Visit approximately 30 days after the Final Visit. This Follow-Up Visit does not need to be performed for subjects who have had a Final Visit conducted \geq 30 days after discontinuation of ABT-888. If a subject is discontinued from the study with an ongoing adverse event or an unresolved clinically significant laboratory result, the site will attempt to provide follow up until a satisfactory clinical resolution of the laboratory result or adverse event is achieved. In the event that a positive result is obtained on a pregnancy test for a subject during the study, the administration of study drug to that subject must be discontinued immediately.

8.5.2 Discontinuation of Entire Study

The investigators may terminate this study provided that written notice is submitted at a reasonable time in advance of the intended termination. The following procedures for discontinuation will be followed:

- 1) If the investigators have decided to prematurely discontinue the study, the investigators will promptly notify in writing the IRB of the decision and give detailed reasons for the discontinuation.
- 2) The principal investigator must promptly notify the enrolled subjects of the premature discontinuation and administer appropriate treatments such as replacement of protocol therapy, if applicable, by other appropriate regimens.

9.0 SAFETY VARIABLES

The Principle Investigator or Sub-investigators will assess adverse events, laboratory data and vital signs throughout the study. Adverse events will be assessed by NCI CTCAE Version 4.0.

http://ctep.cancer.gov/protocolDevelopment/electronic_applications/docs/ctcaev4.pdf

9.1 Adverse Events

The investigator will monitor each subject for clinical and laboratory evidence of adverse events on a routine basis throughout the study. The investigator will assess and record any adverse event in detail including the date of onset, event diagnosis (if known) or sign/symptom, severity, time course, duration and outcome, relationship of the adverse event to study drug, and any action(s) taken. For serious adverse events not considered "probably related" to study drug, the investigator will provide an "Other" cause of the event. For adverse events to be considered intermittent, the events must be of similar nature and severity. Adverse events, whether in response to a query, observed by site personnel, or reported spontaneously by the subject will be recorded. All adverse events will be followed to a satisfactory conclusion.

9.2 Data Safety Monitoring Board

The Georgetown Lombardi Comprehensive Cancer Center will be responsible for the data and safety monitoring of this multi-site trial. As this study is an investigator initiated study Phase I/II study utilizing a non-FDA approved drug for which the PI holds the IND it is considered a high risk study which requires real-time monitoring by the PI and study team and quarterly reviews by the LCCC Data and Safety Monitoring Committee (DSMC).

The Principal Investigator and the Co-Investigators will review the data including safety monitoring at their weekly institution based disease group meetings and on monthly teleconferences with participating sites.

All Severe Adverse Events (SAEs) are required to be reported to the IRB. Based on SAEs, the IRB retains the authority to suspend further accrual pending more detailed reporting and/or modifications to further reduce risk and maximize the safety of participating patients.

Progress on the trial and the toxicities experienced will be reviewed by the LCCC Data and Safety Monitoring Committee every 3 months from the time the first patient is enrolled on the study. Results of the DSMC meetings will be forwarded to the IRB with recommendations regarding need for study closure. .

DSMC recommendations should be based not only on results for the trial being monitored as well as on data available to the DSMC from other studies. It is the responsibility of the PI to ensure that the DSMC is kept apprised of non-confidential results from related studies that become available. It is the responsibility of the DSMC to determine the extent to which this information is relevant to its decisions related to the specific trial being monitored.

A written copy of the DSMC recommendations will be given to the trial PI and the IRB. If the DSMC recommends a study change for patient safety or efficacy reasons the trial PI must act to implement the change as expeditiously as possible. In the unlikely event that the trial PI does not concur with the DSMC recommendations, then the LCCC Associate Director of Clinical Research must be informed of the reason for the disagreement. The trial PI, DSMC Chair, and the LCCC AD for Clinical Research will be responsible for reaching a mutually acceptable decision about the study and providing details of that decision to the IRB. Confidentiality must be preserved during these discussions. However, in some cases, relevant data may be shared with other selected trial investigators and staff to seek advice to assist in reaching a mutually acceptable decision.

If a recommendation is made to change a trial for reasons other than patient safety or efficacy the DSMC will provide an adequate rationale for its decision. If the DSMC recommends that the trial be closed for any reason, the recommendation will be reviewed by the Associate Director for Clinical Research at G-LCCC. Authority to close a trial for safety reasons lies with the IRB, with the above described input from DSMC and the AD for Clinical Research.

Of note, the DSMB will also review the safety data of the patients enrolled outside of Georgetown University. The multi-institutional coordinator will be tasked with the job of collecting all primary source documentation for patients enrolled outside of Georgetown University. In addition, the data managers at each site will be entering data into the Georgetown database, so that all data will be available for the DSMB at Georgetown to review. Faxed records should be sent to [contact], with an email to the multi-institutional coordinator and [name] to confirm receipt of those records.

9.3 Definitions

9.3.1 Adverse Event

An adverse event (AE) is defined as any untoward medical occurrence in a patient or clinical investigation subject administered a pharmaceutical product and which does not necessarily have a causal relationship with this treatment. An adverse event can therefore be any unfavorable and unintended sign (including an abnormal laboratory finding), symptom, or disease temporally associated with the use of a medicinal (investigational) product, whether or not the event is considered causally related to the use of the product. Such an event can result from use of the drug as stipulated in the protocol or labeling, as well as from accidental or intentional overdose, drug abuse, or drug withdrawal. Any worsening of a pre-existing condition or illness is considered an adverse event. Laboratory abnormalities and changes in vital signs are considered to be adverse events only if they result in discontinuation from the study, necessitate therapeutic medical intervention, and/or if the investigator considers them to be adverse events.

An elective surgery/procedure scheduled to occur during a study will not be considered an adverse event if the surgery/procedure is being performed for a pre-existing condition and the surgery/procedure has been pre planned prior to study entry. However, if the pre-existing condition deteriorates unexpectedly during the study (e.g., surgery performed earlier than planned) then the deterioration of the condition for which the elective surgery/procedure is being done will be considered an adverse event.

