In a separate study in rats in which ABT-888 was combined with TMZ, observed toxicities were consistent with exacerbation of known TMZ toxicity. Coadministration of TMZ at 16 mg/kg/day and ABT-888 at doses of 12.5 and 25 mg/kg/day (divided BID) resulted in increased toxicity over that observed with TMZ administration alone, affecting bone marrow (manifesting as decreased neutrophils, lymphocytes, and reticulocytes), lymphoid tissues, testes, and ovaries. Recovery of toxicologic findings was observed at the end of a 28-day recovery period (with the exception of the testes). At a higher dose of ABT-888 (75 mg/kg/day divided BID), there was watery diarrhea with histologic changes, including intestinal crypt necrosis, and dose-related hematologic toxicity. Full exposure data for ABT-888 was not obtained in this study as the majority of the plasma was utilized to evaluate the pharmacokinetic profile of TMZ. However, evaluation of selected pharmacokinetic time points was comparable to that noted in previous studies. In these previous preclinical toxicology studies, a dose of 25 mg/kg/day resulted in an exposure that exceeded anticipated clinical efficacious exposure by 1.3 to 4 fold in the male rat and 2.6 to 7 fold in the female rat. ABT-888 resulted in a reversible and non-lethal exacerbation of TMZ hematologic toxicity in the rat at doses that, in previous studies, resulted in exposures that were similar to or greater than the maximally efficacious exposure (AUC) in the melanoma murine model. However, even in the most sensitive preclinical model (dog) seizures were not seen at exposures less than or equal to 8-fold above the preclinical efficacious exposure (AUC). Therefore, hematological toxicity is expected to be the dose-limiting toxicity in the clinic occurring at doses and exposures well below those at which seizures have been observed. Subjects in the clinic will be carefully monitored for hematologic abnormalities.

5.5 5-Fluorouracil and Oxaliplatin

5.5.1 5-Fluorouracil

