8.3.2.6 Clinical Laboratory Tests

All subjects will undergo the laboratory assessments outlined in Table 3.

- 1) Hematology and chemistry samples will be collected at the Screening Visit, and on Day 1 of each cycle and at the Final Visit. For Day 1 of each cycle after Cycle 2, hematology and chemistry samples may be collected up to 48 hours prior to the scheduled visit.
- 2) PT/INR and PTT will be collected at Screening.

Laboratory samples for this study will be assessed using the certified laboratories at investigators' institutions, or at a clinical laboratory such as Quest or LabCorp. The PI or sub-investigator will review, initial and date all laboratory results. Any laboratory value outside the reference range that is considered clinically significant by the investigator will be followed as appropriate. Clinically significant laboratory values will be recorded as adverse events if they meet the criteria as specified in Section 9.

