9.3.8 Toxicity Management

For the purpose of medical management, all adverse events and laboratory abnormalities that occur during the study must be evaluated by the investigator. The table of clinical toxicity grades modified from the National Cancer Institute Common Terminology Criteria for Adverse Events, Version 4.0, available at http://ctep.cancer.gov/protocolDevelopment/electronic_applications/docs/ctcaev3.pdf

is to be used in the grading of adverse events and laboratory abnormalities that are reported as adverse events, each of which will be followed to satisfactory clinical resolution. A drug-related toxicity is an adverse event or laboratory value outside of the reference range that is judged by the investigator to be either "possibly related" or "probably related" to the study drug. A toxicity is deemed "clinically significant" based on the medical judgment of the investigator.

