13.5.4.3 Adverse Events

Analyses of adverse events (and Serious adverse events) will include only "treatment-emergent" events, i.e., those that have an onset on or after the day of the first dose of study drug. Analyses will not include those that have an onset greater than 30 days after the last dose of study drug. Treatment emergent adverse events will be summarized by system organ class and preferred term according to the MedDRA adverse event coding dictionary. The percentage of subjects experiencing an adverse event at a given severity, NCI CTCAE toxicity grade, and relationship to study drug will be provided.

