13.5.4.5 Longitudinal Analyses of Laboratory and Vital Signs Data

Changes and/or percent changes from baseline will be analyzed for each scheduled post-baseline visit and for the final visit for blood chemistry and hematology parameters, as well as urinalysis and vital sign parameters. If more than one measurement exists for a subject on a particular day, then an arithmetic average will be calculated. This average will be considered to be that subject's measurement for that day. Post-baseline measurements more than seven days after the last dose of study drug will not be included. Subjects that do not have a baseline measurement or do not have any post-baseline measurements will not be included.

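### Section 9.3.1 lets a Grade 3/4 cytopenia managed only by a hold or dose reduction go unrecorded as an adverse event, at odds with section 9.4, and no planned table would recover it

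*Combined protocol and SAP*

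**What the plan says.** Section 9.3.1 opens broadly: "An adverse event can therefore be any unfavorable and unintended sign (including an abnormal laboratory finding), symptom, or disease temporally associated". Later in the same paragraph it narrows this for laboratory data: "Laboratory abnormalities and changes in vital signs are considered to be adverse events only if they result in discontinuation from the study", or if they "necessitate therapeutic medical intervention, and/or if the investigator considers them to be adverse events". Section 8.3.2.6 applies the same filter: "Clinically significant laboratory values will be recorded as adverse events if they meet the criteria as specified in Section 9". Section 9.3.8 directs CTCAE grading at the "grading of adverse events and laboratory abnormalities that are reported as adverse events".

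Section 9.4 uses the term differently. Section 9.4.3.3.1 refers to adverse events that cause one of the drugs to be interrupted. Tables 6A and 6B list the ANC, platelet and hemoglobin triggers in a column headed as adverse events, and respond to them with a hold, weekly blood counts and dose reductions.

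For the analysis, section 13.5.4.3 promises: "The percentage of subjects experiencing an adverse event at a given severity, NCI CTCAE toxicity grade, and relationship to study drug will be provided". Section 13.5.4.5 covers laboratory data separately: "Changes and/or percent changes from baseline will be analyzed for each scheduled post-baseline visit" and for the final visit. It drops values taken more than seven days after the last dose.

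**The concern.** Low blood counts are the toxicity the protocol most expects. Section 5.4.4 states that "hematological toxicity is expected to be the dose-limiting toxicity in the clinic". Section 5.5.3 warns that FOLFOX myelosuppression can delay treatment and may be an issue with ABT-888, and drops the 5FU bolus for that reason. Section 5.7 reports Grade 4 thrombocytopenia or neutropenia when ABT-888 was given with temozolomide.

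Tolerability and safety of the combination is a stated secondary objective (section 7.2.1). If the usual way of managing a low count does not make it an adverse event, the published Grade 3/4 hematologic rate depends partly on each investigator's recording habit.

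**Working it through.** No figure in the plan is at issue, so there is none to reproduce. The Simon rule counts responses and does not use the adverse event definition. The check follows one event through the text: an asymptomatic Grade 3/4 neutropenia or thrombocytopenia in Phase II that leads to a hold and a dose reduction, with no transfusion, growth factor or antibiotic.

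1. **Is it an adverse event under 9.3.1?**
   - Discontinuation from the study: no. Section 9.4.3.3.1 stops treatment until recovery, and Table 6B keeps the patient on study even at a third occurrence. (In Table 6A, for Phase I, a third occurrence of the most severe hematologic category takes the patient off study.)
   - Therapeutic medical intervention: the term is undefined. On a narrow reading (something given to treat the abnormality), no. On a broad reading (any change in treatment), yes.
   - Investigator judgement: optional.

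   On the narrow reading, recording rests on judgement alone.

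2. **Is it an adverse event under 9.4?** By the wording of 9.4.3.3.1 and the column heading of Tables 6A and 6B, yes. The two sections disagree, and nothing says which governs.

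3. **If it is not recorded, does an analysis recover it?**
   - Section 13.5.4.3: no, because its percentages are built from adverse events.
   - Section 13.5.4.5: no. It gives change from baseline by scheduled visit, with no CTCAE grade, shift or worst value per patient. Weekly counts taken during a hold are not scheduled visits, and values beyond seven days after the last dose are excluded, whereas 13.5.4.3 follows adverse events for 30 days.
   - Table 3 adds a smaller gap: Day 1 of even-numbered cycles from cycle 4 has a blood count but no adverse event evaluation.

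4. **Does it touch dose finding?** No. Section 9.4.1 defines the hematologic DLTs directly by grade, for Phase I cycle 1 only.

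5. **Size, as illustration only.** The documents give neither a Grade 3/4 rate nor a recording share, so both are assumptions here. Let *h* be the proportion of patients whose only Grade 3/4 cytopenia is managed by hold or reduction, *t* the proportion with a Grade 3/4 cytopenia that is treated and so recorded, and *c* the share of the first group that is recorded.

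   True rate = *t* + *h*. Reported rate = *t* + *h* × *c*. Shortfall = *h* × (1 − *c*), whatever the value of *t*.

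| Assumed *h* | *c* = 100% | *c* = 75% | *c* = 50% | *c* = 25% |
|---|---|---|---|---|
| 20% | 0 | 5 points | 10 points | 15 points |
| 30% | 0 | 7.5 points | 15 points | 22.5 points |
| 40% | 0 | 10 points | 20 points | 30 points |
| 50% | 0 | 12.5 points | 25 points | 37.5 points |

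With 48 Phase II patients, the nonzero cells run from 0.05 × 48 = 2.4 to 0.375 × 48 = 18 expected patients missing from the rate. This shows how the shortfall behaves and does not forecast it.

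**The case against.** The strongest answer is that the protocol already calls these events adverse events, in 9.4.3.3.1 and in the tables an investigator would consult when counts fall. There is more on that side:

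- A hold or dose cut may count as therapeutic medical intervention.
- Section 9.3.8 requires the investigator to evaluate every laboratory abnormality and lets an out-of-range value be a drug-related toxicity.
- Section 9.3.2 gives blood dyscrasias without hospital admission as an example of an important medical event.
- Cytopenias treated with transfusion, an erythropoietin analog or pegfilgrastim meet the intervention trigger.
- A central coordinator reviews study-related adverse events (8.4.1), and monthly calls between sites cover toxicity (8.4.4).

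Much of this stands. It makes recording likely in many cases, and it makes the defect an inconsistency between sections, not a clean exclusion. It does not make recording required, and it supplies no graded laboratory table.

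A reader might infer three stronger things that the documents do not support:

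- **That the reported rate is certainly biased downward and differs by site.** If every investigator records these events, nothing is lost, and no recording share is given for any site.
- **That the DSMC cannot see these events.** Sections 9.2 and 8.4.3 put all data in one database available for its review. What is missing is a specified summary.
- **That the recommended Phase II dose is in doubt.** The DLTs do not pass through 9.3.1.

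The statement in 5.4.4 also rests on preclinical work with temozolomide, and a single-arm trial would not isolate the effect of adding ABT-888 even with complete recording.

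**Conclusion.** The point holds as an inconsistency with a possible one-directional effect. Sections 9.3.1 and 9.4 disagree on whether a cytopenia managed only by hold or reduction is an adverse event. Under 9.3.1 it can go unrecorded, and neither planned safety analysis would recover it. The Phase II and later-cycle Grade 3/4 hematologic rate can therefore be understated. Omission can only lower that rate, but the amount cannot be estimated from the documents and may be nil.

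This rests on two assumptions: that 9.3.1 governs recording, as 8.3.2.6 implies, and that a hold or reduction is not itself a therapeutic medical intervention. The primary endpoint, the Simon rule and the Phase I cycle 1 DLT assessment are untouched. The change is worth making because it is cheap and takes discretion out of a stated safety objective.

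**What to change.** These are reporting changes only. No dose or treatment rule changes.

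- **Section 9.3.1:** reconcile it with 9.4 by adding that a laboratory abnormality is recorded as an adverse event if it is CTCAE Grade 3 or higher, or if it leads to a hold, delay or reduction of any study drug.
- **CTCAE version:** name one throughout. Sections 9.0 and 9.3.8 cite 4.0 (the link in 9.3.8 points to a version 3 file), while 9.3.3 cites 3.0. A grade-based trigger needs a single scale.
- **Section 13.5.4.5:** add a table of the worst post-baseline CTCAE grade per patient for ANC, platelets and hemoglobin, and for the chemistry values already collected. Derive it from all recorded values, including unscheduled ones, through 30 days after the last dose. State that the seven-day exclusion does not apply to this table.
- **DSMC reports:** include that table in the quarterly review.

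The cost is one clause, one version correction and one derived table from existing data. The downside is more adverse event entries for the sites and a hematologic toxicity rate that may look less favourable.
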